## 6.4 Time Period and Frequency for Event Assessment and Follow-Up

All AEs including local and systemic reactions not meeting the criteria for SAEs will be captured on the appropriate CRF. Information to be collected includes event description, time of onset, clinician's assessment of severity, relationship to study product (assessed only by those with the training and authority to make a diagnosis), and time of resolution/stabilization of the event. All AEs occurring while on study must be documented appropriately regardless of relationship.

Any medical condition that is present at the time that the participant is screened will be considered as baseline and not reported as an AE. However, if the study participant's condition deteriorates at any time during the study, it will be recorded as an AE and all AEs will be recorded in the data collection system throughout the study.

Changes in the severity of an AE will be documented to allow an assessment of the duration of the event at each level of severity to be performed. AEs characterized as intermittent require documentation of onset and duration of each episode.

The PI will record all reportable events with start dates occurring any time after informed consent is obtained until 7 (for non-serious AEs) or 30 days (for SAEs) after the last day of study participation. At each study visit, designated study personnel will inquire about the occurrence of AE/SAEs since the last visit. Events will be followed for outcome information until resolution or stabilization.

#### **6.4.1 AEs and SAEs Reporting**

All AEs and SAEs must be reported to the local IRB per their guidelines.

Data Safety Monitoring Plan: The Data Safety Monitoring Board (DSMB) will be monitoring the subjects in real time for adverse events. Accumulated data and adverse events will be reviewed at 30-day intervals. Additionally, data will be reviewed for safety after the first 20 subjects are enrolled, then after the next 50 and then in increments of 50 thereafter. If there is an unanticipated safety signal, stopping the study will be considered. A summary of the outcomes of these reviews will be submitted to the IRB.

The DSMB will consist of the following members:

- [name], MD, DOIM-Infectious Disease, will chair the DSMB for this study.
- CTSC biostatistician as assigned based on demand from other clinical trials.
- Medical ethics or legal – [name] or [name]
- Critical care – [name] or designee. Cannot be participating in the clinical trial.

## **7 Statistical Considerations**

### **7.1 Statistical and Analytical Plans (SAP)**

All data will be summarized using appropriate descriptive statistics, including mean, median, standard deviation, and range for continuous variables and frequency and proportions for categorical variables. Data will also be summarized graphically.

### **7.2 Statistical Hypotheses**

We will test the null hypothesis that the positive SARS-CoV-2 rate is the same among participants who opt to take HCQ as among participants who opt not to take HCQ. The alternative hypothesis is that the positive SARS-CoV-2 rate differs between the groups.

### **7.3 Analysis Datasets**

The primary analysis data set will consist of positive SARS-CoV-2 outcomes for all enrolled participants. Sensitivity analyses will be conducted using the subset of HCQ participants who complete their entire course of treatment.

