**Protocol Summary**

Title	Off label study to evaluate the efficacy of hydroxychloroquine as prophylaxis to prevent severe acute respiratory syndrome coronavirus 2 (SARS-CoV-2) infection among Health Care Workers (HCWs) who are at high risk of occupational exposure to SARS-CoV-2 Short Study Title: COVID-19 HCWP HCQ Study
Brief Summary	The HCW Prophylaxis (HCWP) Study, single, open and off label intervention study. Up to 350 participants will be assigned to group that takes HCQ or group that opts to not take study medication. Participants will be UNM HEALTH SYSTEM HCW at high risk for occupational exposure to SARS-CoV-2. Study timepoints will include Day 1 screening/enrollment, 30 day, 60 day, and 90 day assessments. Questionnaires will be collected in all timepoints.
Phase	Off label use of HCQ
Primary Objectives	To evaluate the efficacy of hydroxychloroquine (HCQ) for prophylaxis (HCWP) to prevent severe acute respiratory syndrome coronavirus 2 (SARS-CoV-2) infection among Health Care Workers High Risk of Occupational Exposure to SARS-CoV-2
Methodology	The Health Care Worker Prophylaxis (HCWP) Study, single, open and off label intervention study
Primary Endpoint	Number of HCW who test positive for SARS-CoV-2 while in the trial as determined by polymerase chain reaction assays from standard of care swaps.
Study Duration	12 months
Participant Duration	Participant Study period: up to 90 days for both groups, inclusive of those who elect to convert from Group B to Group A.
Duration of IP administration	Up to 90 days
Population	Total number of participants: Up to 350 UNM HEALTH SYSTEM health care workers with high risk of occupational exposure to SARS-CoV-2 Group A: up to 275 (HCW choose to be provided HCQ) Group B: up to 75 (HCW choose not to be provided HCQ)
Study Sites	UNM HEALTH SYSTEMS
Number of participants	Up to 350
Description of Study Agent/Procedure	Hydroxychloroquine- oral administration 
 
• Duration: up to 90 days or until meeting study termination criteria
 
• Loading dose: 600 mg once for the first day
 
• Maintenance dose: 200 mg, daily
 
 
Hydroxychloroquine is licensed for the chemoprophylaxis and treatment of malaria and as a disease modifying antirheumatic drug. It has a long history of being safe and well tolerated at typical doses. HCQ has antiviral activity in vitro against coronaviruses, and specifically Covid-19.

Key Procedures	Questionnaires

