#### 4.2.1.1 Inclusion Criteria

1. Men or women  $\geq 18$  years of age who are UNM HEALTH SYSTEM health care workers and are asymptomatic for known presenting symptoms of SARS-CoV-2:
2. UNMHS HCWs include: MD/DO, NP, RN, and respiratory therapists working in ED, Pediatric ED, Urgent Care, Pediatric Urgent Care or on Covid-19 units. Study PI's will consider study enrollment of HCWs from other settings, for example certain outpatient clinics or inpatient units.
3. Are not positive for SARS-CoV-2 testing
4. Willing and able to comply with survey completion, scheduled visits, treatment plan, and other study procedures
5. Willing and able to provide informed consent

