#### 4.7.1.3 Supplies

HCQ will be dispensed at the time of study enrollment or as soon as practical thereafter, after subjects have completed all Screening procedures and signed informed consent. The drug will be requested from the UNMH Research Pharmacy on the 4th floor or other approved clinical trial pharmacy locations where it may be stored. Drug will be dispensed to subjects by qualified study personnel. There will be no cost to the participants. Currently there is a sufficient amount of HCQ. This study will not deplete HCQ from stores or pharmacies. HCQ supplies for standard of care and patients with preexisting indications will not be compromised by execution of this study.

Dispensing schedules

- 33 pills (200 mg oral tablet) at enrollment
- 30 pills (200 mg oral tablet) at 30 and 60 day visits

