## 5 Study Procedures and Schedule

### 5.1 Study Procedures/Evaluations

#### 5.1.1 Study Specific Procedures

##### Employee Exposure Survey and Aerosol Generating Procedures (Appendix A)

Participants from both Group A and B will be asked to complete the Employee Exposure Survey. This online instrument asks health care providers currently working in at risk units to report symptoms or exposures (eg. AGPs) related to their encounters with patients who have or are suspected of Covid-19. These HCWs are reminded to complete the Survey once per day. The link to this REDCap survey is currently being emailed to UNMHSC HCWs and they can access it through widely distributed QR codes. Given its active use, this survey will not add additional stress or workload to study participants. Additional study specific questions will be added to this survey and the data is linked to REDcap a database.

Confirmation of Pregnancy in Women of Childbearing Potential: We will document in subject's research record whether they are pregnant based on self-report and date of last menses (at Screening and follow-up visits). Pregnancy is not a contraindication for receiving HCQ.

A list of potential Aerosol Generating Procedures (AGP) is also provided in Appendix A.

Subjects will only be asked to complete SARS-CoV-2 testing at study enrollment and the 30, 60 and 90 day follow up points, with a 7-day window after each time point to complete the testing.

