### 5.2 Study Schedule

#### 5.2.1 Schematic of Study Design

##### Schematic of Study Design

**Schedules of Activities for COVID-19 HCWP HCW HCQ Study**

Task	Screening/ Baseline	Daily (existing required survey)	30 Day (± 7days)	60 Day (± 7days)	90 Day (± 7days)	Early Termination or Clinically Suspected SARS- CoV-2
Consent	X					
Health history	X					
Exposure Survey (online)	X	X				X
Swab* for SARS-CoV-2 and plasma/serum sample	X		X	X	X	X
Hydroxychloroquine dosing initiation	X					
Adverse Events		X	X	X	X	X

\*Lab has confirmed ability to test samples from week over next weekend. Estimate up to 50 total per week (25 Sat, 25 Sun). Lab has also agreed to bank plasma and serum samples for delayed analysis.

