### 7.4.2 Analysis of the Primary Efficacy Endpoint(s)

Detection of SARS-CoV-2 RNA by PCR will be the primary endpoint and will be compared between treatment groups (prophylaxis vs. no prophylaxis). Positive SARS-CoV-2 will be defined as a binomial variable (i.e., positive SARS-CoV-2 or no positive SARS-CoV-2) and analyzed using Wilcoxon rank analysis. Potential confounders of the primary endpoint will be addressed by using standard statistical matching techniques, such as propensity score matching, and logistical regression to assess for confounding by exposure risk, demographic factors and comorbidities that are known or suspected to affect the likelihood of developing SARS-CoV-2 infection.

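### Infections already present at the baseline swab can be counted as primary events, because the primary set is all enrolled participants and the schedule permits enrolment and HCQ start before the result.

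*Combined protocol and SAP*

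**What the plan says.** On what is counted:
- Section 7.3, Analysis Datasets: "The primary analysis data set will consist of positive SARS-CoV-2 outcomes for all enrolled participants". The only sensitivity set is the HCQ participants who finish treatment.
- Protocol Summary, primary endpoint: "Number of HCW who test positive for SARS-CoV-2 while in the trial".
- Section 7.4.2: "Detection of SARS-CoV-2 RNA by PCR will be the primary endpoint", treated as a yes/no variable.

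On eligibility and timing:
- Section 4.2.1.1, criterion 3: "Are not positive for SARS-CoV-2 testing". No test, date or sample is named.
- Section 5.1.1: "Subjects will only be asked to complete SARS-CoV-2 testing at study enrollment and the 30, 60 and 90 day follow up points". The tests need not fall exactly on those days, since up to a week more is allowed for each, enrolment included. Section 5.3 repeats this window and lists baseline among the time points.
- Section 5.2.2 allows screening and enrolment on one day.
- The schedule in 5.2.1 puts the baseline swab and the start of HCQ in the same column. Its footnote says: "Lab has confirmed ability to test samples from week over next weekend".
- Section 4.7.1.3: "HCQ will be dispensed at the time of study enrollment or as soon as practical thereafter". The stated conditions are finished screening and a signed consent; a test result is not among them.
- Section 4.6 lists PCR-confirmed status as a reason for withdrawal or termination. It does not mention removal from the analysis set.

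**The concern.** The primary objective in section 3 is prevention of infection. An infection already present when the baseline swab is taken cannot have been prevented by a drug started at or after that visit. If such infections are counted, they add the same kind of event to both groups and pull the comparison toward no effect.

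Participants choose their own group, so baseline prevalence may also differ between groups. The bias can then run in either direction. The adjustment in 7.4.2 covers exposure risk, demographic factors and comorbidities, but not infection at entry. Requiring participants to be asymptomatic does not close the gap, because section 1 itself says infection can be asymptomatic.

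Two analysts following the text could also count different numbers of primary events from the same data. In an open-label study that choice might be made after the results are visible.

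**Working it through.** **Does the text allow it?** The first study swab is taken at enrolment. The week's samples are tested over the following weekend. Screening and enrolment may share a day, and HCQ is dispensed then or soon after. No section makes enrolment or dosing wait for the result, so a worker never tested before can meet criterion 3. If that worker's baseline swab is later positive, 7.3 keeps the worker in the set and the endpoint wording counts the result.

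**Inputs.**
- From 7.5: 35% control and 20% HCQ, two-sided alpha 0.05.
- From 4.2.1: group maxima of 275 (HCQ) and 75 (control).
- Assumed, not in the documents: baseline prevalence b of 1–5%, and a lower control risk of 10%.
- The 35% and 20% are taken as new-infection risks among baseline negatives.

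**Formulas.** With baseline positives counted, the observed risk is b + (1 − b)p. Power is Φ[(|p₁ − p₂| − 1.96·SE₀)/SE₁], where SE₀ uses the pooled proportion and SE₁ the separate proportions.

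**The plan's own figure.** For 230/120 the pooled proportion is 0.2514, SE₀ = 0.0489 and SE₁ = 0.0509. Then (0.15 − 1.96 × 0.0489)/0.0509 = 1.065, giving power 0.857. Section 7.5 states 80%, so its figure is mildly conservative. The point does not rest on it.

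**Equal baseline prevalence, 275/75.** With b = 0 the pooled proportion is (75 × 0.35 + 275 × 0.20)/350 = 0.232, SE₀ = 0.0550 and SE₁ = 0.0601. Then (0.15 − 0.1078)/0.0601 = 0.702, giving power 0.759.

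| b | Control | HCQ | Difference | Risk ratio | Power, counted | Power, excluded |
|---|---|---|---|---|---|---|
| 0 | 0.350 | 0.200 | 0.150 | 0.571 | 0.759 | 0.759 |
| 1% | 0.3565 | 0.208 | 0.1485 | 0.583 | 0.743 | 0.755 |
| 2% | 0.363 | 0.216 | 0.147 | 0.595 | 0.728 | 0.751 |
| 5% | 0.3825 | 0.240 | 0.1425 | 0.627 | 0.681 | 0.739 |

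The last column keeps 35% versus 20% and shrinks both groups by the factor 1 − b. Baseline positives number 350 × 0.01 = 3.5 to 350 × 0.05 = 17.5.

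**If infection is rarer.** Take a control risk of 10% and the same true ratio, so HCQ risk is 0.10 × 0.571 = 0.0571.
- At b = 1%: 0.0666/0.109 = 0.61. Baseline infections are 3.5/(275 × 0.0666 + 75 × 0.109) = 13% of events.
- At b = 5%: 0.1043/0.145 = 0.72. They are 17.5/(275 × 0.1043 + 75 × 0.145) = 44% of events.

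**Unequal baseline prevalence with no drug effect.** Assume 5% in Group A and 2% in Group B, at 275/75.
- New-infection risk 35%: 0.3825/0.363 = 1.05; two-sided rejection rate about 6.0%.
- 20%: 0.240/0.216 = 1.11; about 6.7%.
- 10%: 0.145/0.118 = 1.23; about 8.0%.

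Reversing the imbalance at 10% gives 0.118/0.145 = 0.81, a false benefit.

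**The case against.** The strongest reply is that the timing is inferred. No section says that dosing precedes the result. Dispensing follows completion of screening procedures and may come later than enrolment. Same-day visits are allowed, not required, and the laboratory footnote describes capacity. Criterion 3, together with the stated aim of preventing conversion (2.1), suggests that a baseline positive was meant to be ineligible.

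This stands as far as it goes. A reader might infer that HCQ always starts before the result, or that criterion 3 has no force; the documents support neither. They permit the sequence without establishing it. But the reply does not rescue the analysis rule, because nothing removes an enrolled participant later found ineligible from the all-enrolled set.

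A second reply concerns size. At the plan's rates the difference falls only from 15.0 to 14.25 points at b = 5%, and the larger distortions need an assumed low infection risk or an assumed imbalance. That also stands, and it limits the severity.

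A third reply concerns the remedy. It is tempting to say that excluding baseline positives cannot add selection bias because the swab predates treatment. The documents do not support this. The 7-day window in 5.1.1 and 5.3 follows each time point, enrolment or baseline included, so some baseline swabs may be taken after the first dose. Excluding on those would condition on a post-treatment result in Group A. The fix must allow for this.

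**Conclusion.** The concern holds as a gap that should be fixed. As written, the primary analysis can count infections that prophylaxis could not have prevented, and criterion 3 does not reliably screen them out.

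At the plan's 35% versus 20% the harm is modest across the assumed 1–5% prevalence. Excluding baseline positives recovers about 1, 2 and 6 points of power at 1%, 2% and 5%. The harm grows if infection is rarer than planned or if the self-selected groups differ at entry. All of these sizes rest on assumed prevalence, and the low-risk cases also on an assumed 10% risk.

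A reader might go further and infer that the primary result would be invalid. The figures at the planned rates do not support that.

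**What to change.** In 7.3 and 7.4.2:
- Define the primary event as the first positive PCR on a swab collected after the baseline swab.
- Restrict the primary set, in both groups, to participants without a positive baseline swab. Report baseline positives by group.
- Keep all enrolled participants as a sensitivity analysis.
- Record each baseline swab date against the first-dose date. Base the exclusion only on swabs collected on or before the first dose or, in Group B, the enrolment date.
- Report positive baseline swabs taken after that date separately by group. State in advance how they enter the main analysis, and run a sensitivity analysis with them counted as events and with them excluded. Without such a rule they would stay in the set as non-events and, if withdrawn under 4.6, might have no later swab.

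Sections 4.2.1.1, 4.7.1.3, 5.1.1, 5.2.1, 5.2.2 and 5.3 on the order of swab, result, enrolment and dosing must be reconciled by the investigators. No clinical rule is proposed here.

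The cost is SAP wording and date recording; the baseline swab is already scheduled. The downside is a primary set about 1–5% smaller under the assumed prevalence. One limit remains: 5.2.3 provides rescreening by form for participants who switch from Group B to Group A and names no swab, so this change does not identify infection present at the switch.

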### 3 Objectives

Primary Objective	Primary Endpoint
To evaluate the efficacy of hydroxychloroquine (HCQ) for prophylaxis to prevent severe acute respiratory syndrome coronavirus 2 (SARS-CoV-2) infection among HCWs at high risk of occupational exposure to SARS-CoV-2 compared to eligible cohort that declines treatment	Frequency of infection with SARS-CoV-2 as determined by positive PCR for the virus on standard diagnostic tests.
Secondary Objectives	Secondary Endpoints
1. To characterize whether high-risk HCW who test positive for SARS-CoV-2 have an asymptomatic infection or report symptoms of COVID-19 in the 4 weeks preceding positive SARS-CoV-2	1. Symptom questionnaires performed once daily as currently mandated for HCW in high risk settings within UNMHS.
2. Determine role of occupational health exposure risk level on subsequent conversion frequency (mild-moderate-severe)	2. Online survey required once daily for all at risk HCW (existing document)
3. To assess the severity of any SARS-CoV-2 infection after prophylactic treatment with hydroxychloroquine.	3. Symptom questionnaires, Hospital admission rate, ICU admission rate, Mortality rate, PSI score of respiratory compromise
4. To assess the tolerability of hydroxychloroquine prophylaxis of SARS-CoV-2 in this population	4. Incidence of AEs or SAEs related to HCQ at study termination.
Exploratory Objectives	Exploratory Endpoints
1. To determine whether hydroxychloroquine reduces time lost from work	1. Days away from work
2. To assess the compliance of hydroxychloroquine prophylaxis	2. Frequency of missing dose
3. To assess whether HCQ benefits are different for specific AGPs or exposure on certain covid units (MICU v. ED v. covid rule out unit)	3. Frequency of positive test for SARS-CoV-2 related to AGP's or specific Covid-19 units.
4. To compare seroconversion between HCQ-treated and HCQ-untreated subjects on blood or plasma specimens.	4. Serological analyses at 4 times points (baseline, 30,60 and 90 days of study enrollment---with a 7-day window after each time point to complete analyses)

5. Metagenomic next generation sequencing of SARS-CoV-2 isolates detected in subjects	5. Sequence of viral isolates compared to published genomes and community-circulating SARS-CoV-2
---	--

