## 4.6 Participant Withdrawal or Termination

Reasons for early Withdrawal or Termination

- Participants become PCR-confirmed SARS-CoV-2 status
- Participant starts disallowed medication (Group A only)
- Advent of an adverse event which necessitates discontinuation of HCQ (Group A only, see section 6)
- Participant decides to withdraw from the study
- PI discontinues participation due to safety concerns
- Participant decides to withdraw consent
- Participant's primary care provider determines the study is not in participant's best interest
- PI decides to withdraw participant due to non-compliance

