#### 4.7.1.2 Administration

- Loading dose: 600 mg, oral, 1 day
- Maintenance dose: 200 mg, oral, daily, for 90 days

The study will follow the study agent's labeling guidelines except the dosing schedule selected as described above.

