## **5.3 Laboratory Procedures/Evaluations**

Standard diagnostic swabs will be collected from the participants at baseline and at 30, 60, and 90 day follow up points (with a 7-day window after each time point to complete the testing). A portion of any participant sample testing positive for SARS-CoV-2 will also be evaluated with metagenomic next-generation sequencing. Only viral RNA will be sequenced, not human DNA/RNA.

The Executive Director of Research at the UNM Health Sciences Center Office of Research will be working with institutional officials to ensure the use of viral transport media and swabs during the study do not interfere with adequate supplies available for clinical use. A modification will be submitted to clarify who will supply the swabs and the transport media (i.e. TriCore, UNMH).

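### The sensitivity analysis keeps only HCQ participants who finish the course, but infection ends the course, so HCQ infections drop out and the result is biased toward HCQ

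*Combined protocol and SAP*

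**What the plan says.** Section 7.3 (Analysis Datasets) defines two sets. The primary one is inclusive: "The primary analysis data set will consist of positive SARS-CoV-2 outcomes for all enrolled participants". The second is restricted: "Sensitivity analyses will be conducted using the subset of HCQ participants who complete their entire course of treatment". The restriction applies to HCQ participants only. The section states no matching rule for Group B, names no comparator and does not define completion.

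Three other places determine who can complete:

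- Section 4.6 lists, among the reasons for early withdrawal or termination, "Participants become PCR-confirmed SARS-CoV-2 status". Unlike some other items there, it is not limited to Group A.
- The Protocol Summary gives the duration of HCQ as "up to 90 days or until meeting study termination criteria".
- Section 4.7.1.2 describes the course as "Maintenance dose: 200 mg, oral, daily, for 90 days".

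On detection, section 5.3 says: "Standard diagnostic swabs will be collected from the participants at baseline and at 30, 60, and 90 day follow up points". The schedule of activities in section 5.2.1 adds a swab in a column headed "Early Termination or Clinically Suspected" SARS-CoV-2. PCR positivity is the primary endpoint in sections 3 and 7.4.2.

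**The concern.** The event being counted is also an event that stops treatment. If completing means taking the 90-day course, an HCQ participant must stay free of detected infection until the end of the course to enter the subset. Membership then depends on the outcome, in one arm only. Infected HCQ participants leave both the numerator and the denominator, while infected Group B participants stay in both.

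A sensitivity analysis should show whether the primary result holds under a different reasonable choice. This one moves toward HCQ whatever the drug does. Because participants choose their own group, readers will look to supporting analyses, and this is the only sensitivity set that section 7.3 names. A null primary result could be followed by an apparent benefit among participants who finished the drug, and a confounded primary result could appear confirmed. The matching and logistic regression in section 7.4.2 cannot repair this, because the removed infections are no longer in the data.

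**Working it through.** **Plan's own figures.** The plan gives no figure for this analysis. The nearest is in section 7.5: 80% power for 35% versus 20% with two-thirds on HCQ. At 230 versus 120, a pooled two-proportion test gives 85.7%, so the stated figure is somewhat conservative. Nothing below depends on it. The 35% is used only as an upper example, because section 7.5 offers it as an illustration.

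**Inputs from the documents.** Group caps of 275 and 75 (section 4.2.1); a 90-day course (4.7.1.2); scheduled swabs at days 30, 60 and 90 (5.3); two-sided 5% tests (7.4.1).

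**Assumptions.** HCQ has no effect; all of Group B is the comparator; nobody stops for other reasons; risk is equal in the three 30-day intervals; infections first found at the day-90 swab stay in the subset. The 90-day risk R is varied from 2% to 35%.

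**Formulas.**

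- Risk per interval: q = 1 − (1 − R)^(1/3)
- Infections kept per Group A member (last interval only): k = q(1 − q)²
- Share of HCQ infections removed: 1 − k/R
- Rate among completers: k / (k + 1 − R)
- Apparent risk ratio (RR): that rate divided by R

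**Example, R = 35%.** q = 1 − 0.65^(1/3) = 0.134. k = 0.134 × 0.866² = 0.100. Of 275 × 0.35 = 96.3 HCQ infections, 275 × 0.1004 = 27.6 are kept, so 71% are removed. The completer rate is 0.1004 / (0.1004 + 0.65) = 13.4%, against 35% in Group B. RR = 0.38.

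**Results.** False benefit is the share of simulated trials in which a two-sided 5% test significantly favours HCQ.

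| 90-day risk | Completer rate | RR | False benefit, two-proportion test | False benefit, Fisher's exact test |
|---|---|---|---|---|
| 35% | 13.4% | 0.38 | 97% | 97% |
| 20% | 7.2% | 0.36 | 85% | 82% |
| 10% | 3.5% | 0.35 | 60% | 54% |
| 5% | 1.7% | 0.34 | 38% | 35% |
| 2% | 0.7% | 0.34 | 19% | 16% |

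The nominal rate in this direction is 2.5%. With only 75 controls, the two-proportion test on the unrestricted set gives about 3.5% at 5% risk and 4% at 2% risk. Those are the fair baselines for the last two rows.

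**Other timing.** If a fraction f of HCQ infections is kept, the completer rate is fR / (fR + 1 − R).

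| Fraction kept | RR, false benefit at R = 35% | RR, false benefit at R = 10% |
|---|---|---|
| 1/2 | 0.61, 66% | 0.53, 33% |
| 2/3 | 0.75, 31% | 0.69, 17% |
| 0.9 | 0.93, 6% | 0.91, 5% |

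Symptom-triggered swabs act the other way. If half of last-interval infections are found before day 90, k is halved and 83–86% of HCQ infections are removed. At R = 35% the completer rate is 0.0502 / (0.0502 + 0.65) = 7.2%, RR 0.20; at R = 2% the RR is 0.17. If day-90 positives also count as non-completers, the HCQ rate is zero by construction.

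**Different allocation.** With 230 versus 120 and f = 1/3, R = 35% gives 15.2% versus 35% and a false benefit in 97.6% of trials. R = 10% gives 3.6% versus 10% and 66.8%. Adding 20% non-completion unrelated to infection leaves the 15.2% unchanged, with a false benefit in 96.3%.

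**Masking of harm.** With f = 1/3 and control at 35%, the completer rate equals 35% when the true HCQ risk x satisfies (x/3) / (x/3 + 1 − x) = 0.35, so x = 0.35 / 0.567 = 62%. A large harmful effect could look neutral.

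**The case against.** The strongest objection is that completion is undefined. The Protocol Summary gives the duration of HCQ as 90 days or until a termination criterion is met. On that wording, someone who took every dose until a positive PCR has completed the course, and the bias disappears. This reading is possible, but section 7.3 does not adopt it, section 4.7.1.2 describes a 90-day course, and nothing says that infection counts as an event and not as non-completion. An analyst applying the text literally would drop these participants.

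The comparator is also inferred. All of Group B is the natural reading, because only HCQ participants are restricted, but the plan does not say so and every figure above depends on it.

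The size is uncertain and can be small. If infections cluster late and 90% are kept, the RR is 0.90–0.93 and false benefit is 5–6% across risks from 2% to 35%. That requires an unusual concentration at the day-90 swab, but the documents do not exclude it. The direction would change only if other non-completion were strongly tied to infection risk, which nothing in the documents suggests.

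Finally, the primary analysis is sound on this point, no decision rule is tied to the sensitivity analysis, and section 1 says the study is not meant to support a new indication. This limits the consequence. It does not make the analysis informative.

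**Conclusion.** The concern holds. Read with sections 4.6 and 4.7.1.2, section 7.3 removes HCQ infections found before the end of the course and keeps the corresponding Group B infections. The direction, toward HCQ, follows from the text if completion means the 90-day course and Group B is left whole.

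The size rests on assumed risk and timing. Equal risk over time gives an apparent RR of 0.34–0.38 for an inert drug. The possible range runs from a slight shift, when nearly all infections surface at day 90, to an HCQ rate of zero, when day-90 positives are also excluded. As written, the analysis cannot serve as a check on the primary result. It should be corrected before analysis; the all-enrolled primary analysis needs no change on this account.

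**What to change.** Rewrite the sensitivity-analysis sentence in section 7.3 to state four things:

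1. Infection on HCQ does not count as non-completion. Every infection occurring on HCQ stays in the set as an event.
2. Adherence is doses taken divided by doses due up to infection or day 90, whichever comes first, with the threshold for inclusion fixed in advance.
3. The comparator is named.
4. The handling of participants who switch from Group B to Group A (section 5.2.3) is stated. Their participation is capped at 90 days in total, so late switchers may be unable to complete a 90-day course.

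This is an analysis rule only and does not touch when HCQ is stopped.

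**Check of the fix.** Let h and s be constant hazards over the 90 days for infection and for stopping for other reasons. Events are h/(h + s) × (1 − exp(−(h + s))) and non-events are exp(−(h + s)). At R = 10% the HCQ rate is 10.0%, 10.5% and 11.1% when 0%, 10% and 20% stop for other reasons and are excluded. False significant benefit is then 1–3%. Across risks of 2–35% the RR is 1.00 with no other stopping and 1.04–1.12 with 10–20%, slightly against HCQ.

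To remove that remainder, an optional per-protocol version can censor at HCQ discontinuation for other reasons and censor Group B at switch. It needs a person-time or time-to-event method, which section 7.4.2 lacks, and a rule for dating infections found only at scheduled swabs.

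**Cost.** A short rewrite and modest extra analysis. Section 3 lists "Frequency of missing dose" as an exploratory endpoint, but the schedule in section 5.2.1 has no adherence row, so the team must confirm that missed doses are recorded by date. The optional version costs more.
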